5.7 Withdrawal of Participants

This is not a treatment study; withdrawing or being terminated from this study will not have an impact on participant safety. A study clinician or the PI may withdraw a participant without their consent if he or she feels that it is not in a participant’s best interest to continue in the. All data previously collected from participants who withdraw, or are withdrawn, or lost to follow-up will be kept and may be used in the study data analysis. If participants choose to withdraw, miss multiple visits or their participation is terminated, we will contact them to request that they return the study provided footwear; a mailer will be provided if needed. We will make up to three contact attempts to recover the study equipment. Participants may withdraw at any time by informing the Research Coordinator and/or the PI.

6.0 Reporting

All safety information on Adverse Events (AEs), Serious Adverse Events (SAEs), unanticipated events or problems, and protocol deviations will be collected. This information will be collected at study visits and whenever participants call to report a problem. It will be collected on VA IRB forms (Report of a SAE and/or Problem Form), or Report of Problems (ROP) Form. Safety data will be collected on an as-needed basis and will begin upon enrollment into the study. Any anticipated AEs will be recorded on a log sheet and reported annually with the CRQ. Although the risks identified in this study are relatively minimal, we will tabulate a list of any such reports that occur during the study and compare it with corresponding data available in the literature. Participant pain ratings will be collected weekly which will help us to monitor any significant changes. This will allow us to analyze how much of an increased risk was due to the administered protocol. Also please note, the anticipated maximum radiation dosage (0.40 mSv) is far below any dose that would have a measurable effect on participants. After each report of an AE, SAE or an unanticipated problem, we will evaluate study procedures for previously-assessed risks, and will determine whether any changes to the protocol are necessary to minimize risks. The study will be suspended until these changes have been fully implemented and approved by the IRB.

If we become aware of relevant findings or information that may affect participants’ health or welfare we will contact participants by phone and/or a letter to notify them.

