5.5 Study Visits, Data Collection, and Risk Management

Participants can be enrolled in one of three study groups for this project. The specific procedures for each item are outlined below.

Visits at the VA Puget Sound may last up to 4 hours each. Participant schedules and the accessibility of facility resources may extend the study timeframe beyond these estimates. Study visits will be scheduled by contacting the participants on phone, or during in-person contacts. We may contact participants with appointment and/or at home activity reminders via email or phone.

Study group 1: One day visit

Participation will be at the VA Puget Sound and last up to 4 hours wearing the participants own or study provided footwear during the activities. Activities may include a Screening, Functional assessments, CT scan with pregnancy test, Qualitative questions, Brief Pain Rating, and a Biplane assessment with one or more interventions including barefoot, their own footwear, a modified shoe (such as a rocker bottom shoe), an orthotic device (such as an AFO), or a control shoe provided by the researchers.

Study group 2: Take home portion only (~3 months)

Participants with ankle OA will conduct a initial visit that will include a Screening, Functional assessments, CT scan with pregnancy test, Questionnaires, Qualitative questions, and Brief Pain Rating followed by a 3 month intervention at home intervention, that will include three additional visits to the VA. Timeline and assessments during those visits is described below.

Study group 3: Take home portion with Biplane (~3 months)

This study group is similar to Study group 2, however it does include three biplane assessments over the three additional visits.

Study group 4: Remote take home only (~ 3 months)

This study group is similar to Study group 2, however all procedures will be done remotely. Participants with ankle OA will conduct a initial assessment that will include a Screening, Functional assessments, Questionnaires, Qualitative questions, and Brief Pain Rating followed by a 3 month at home intervention, that will include three additional assessments. Timeline and assessments during those assessments is described below. In addition, we will ask you to wear a StepWatch Activity Monitor (a step counter) and to do brief weekly pain ratings, and daily pain rating and pain medication use over the course of the entire study.

Photos and video

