On day-1 of the first at home period, participants will wear the study footwear for one hour, then for two hours on day-2, three hours on day-3, then continue adding one hour of wear per day until the seventh day is reached. For the next two weeks, participants will wear the study footwear throughout the day during their normal daily activities. Participants will wear the StepWatch throughout this 3-week period. Each day participants will receive two messages either via email or with Ilumivu from the study staff, one in the morning, reminding the participant to wear the selected

footwear for the suggested number of hours, and one in the evening, reminding the participant to record the number of hours he/she has worn the selected footwear.

Once per week we will call/email/ message through Ilumivi (which ever the participant prefers) participants to check in and complete the Brief Pain Rating and Qualitative assessment.

Participants will be instructed to contact us if they have questions or if the study footwear is painful/uncomfortable. We will address any issues on an as needed basis, which may require additional visits to the VA.

If a proper and comfortable fit cannot be achieved with a footwear condition, then participants may wear their own shoes for a one-week washout period (while continuing other study procedures) and we will move them to the next footwear condition if they wish to continue their participation. If we determine that it is not in the participant's interest to continue in the study he/she will be withdrawn.

Assessment 2

After the 2-week continuous wear period, participants will come to the VA Puget Sound with the StepWatch and study footwear. The StepWatch data will be downloaded and participants will complete the Brief Pain Rating, Qualitative assessment, Questionnaires, and Functional assessments. For those enrolled in Study group 3, the Biplane assessment will be conducted during this visit using the current footwear condition.

Participants will be given instructions for the second footwear condition.

In Home/Community Footwear Condition 1 Washout Period (1 week)

For the next week, participants will be asked to wear their own self-selected footwear, continue wearing the StepWatch and complete the weekly pain rating over the phone.

In Home/Community – Footwear Condition 2: Acclimation & Continuous Wear Period (3 weeks)

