Stress and Inflicted Insight: Participants may feel a mild level of emotional stress if they find it inconvenient to travel to the VA for study visits, or if they have difficulty sitting or standing still during the CT scan. It is possible that we could discover that female participants are pregnant. It is also possible that the imaging procedures (CT scans, and fluoroscopic images) could reveal that a participant has a serious health problem or anatomical abnormality (e.g., bone cancer). Potential participants will be screened during the telephone call, or in person screening, regarding their willingness to be made aware of the pregnancy test result and/or potential health problems discovered by the imaging procedures. Those who are not willing to be told about this information will be excluded from the study. Additionally, in the consent form, participants will again be made aware of this possibility and given the option to decline participation in the study if they choose. If a participant is determined to be pregnant and/or if we see an unexpected abnormality in a participant's radiological images we will advise them to follow up with their regular health care provider.

Wearing Study Assigned Footwear and the StepWatch

At Home Trip and Fall: There is a risk of tripping and falling while wearing the study assigned footwear at home and in the community, but this risk is not greater than that of daily life.

Increased Foot or Ankle Pain, Soft Tissue Irritation: There is a risk that the study assigned footwear could increase foot or ankle pain. There is a risk of minor discomfort, soft tissue irritation or skin break down (e.g. skin blister) in response to wearing the study assigned footwear and the SAM. Participants will be instructed to inform us if they feel discomfort or pain when wearing the control shoes, RB shoes, or AFO for the first time. Participants will have the opportunity to walk around to

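### Between assessments, safety collection is passive: the weekly contact has no stated fall or skin question, and section 6.0 does not say whether group 4's remote assessments count

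*Combined protocol and SAP*

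**What the plan says.** Section 6.0 (Reporting) names two routes for adverse events, serious adverse events, unanticipated problems and deviations: "This information will be collected at study visits and whenever participants call to report a problem". It adds: "Safety data will be collected on an as-needed basis and will begin upon enrollment into the study". The only weekly item it links to safety is pain: "Participant pain ratings will be collected weekly which will help us to monitor any significant changes". On use of the data, it says "we will tabulate a list of any such reports that occur during the study and compare it with corresponding data available in the literature", and it expects to judge how far the protocol itself raised risk.

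Section 5.5, under the heading on wearing the assigned footwear and the StepWatch, names two take-home risks besides pain. One is falls: "There is a risk of tripping and falling while wearing the study assigned footwear at home and in the community". The other is skin: "There is a risk of minor discomfort, soft tissue irritation or skin break down (e.g. skin blister" is the example given. The fall risk is stated to be no greater than in daily life.

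During wear periods, section 5.5 has staff reach out once a week to "participants to check in and complete the Brief Pain Rating and Qualitative assessment". In washout weeks only the weekly pain rating is named. Of group 4 it says: "This study group is similar to Study group 2, however all procedures will be done remotely". That group has an initial assessment and three further ones.

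**The concern.** The protocol names falls and skin breakdown as hazards of home wear, yet shows no question about either. Its safety rule relies on assessments three or four weeks apart and on participants deciding to call. A contact that could carry the questions already takes place every week but is not named as a safety collection point.

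At stake is the use that section 6.0 makes of the data. A list of events to be compared with the literature is only as good as its ascertainment. Attributing added risk to the protocol requires each event to be dated and tied to the footwear worn. Section 6.0 also makes each report the trigger for a review of procedures, so an event nobody reports prompts no review.

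**Working it through.** **1. Schedule.** Section 5.5 gives three wear periods of 3 weeks and two washouts of 1 week: 3×3 + 2×1 = 11 weeks. This reproduces the stated length of 11 weeks.

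**2. Scheduled safety points now.** Each follow-up assessment closes a wear period:
- Assessment 2: week 3.
- Assessment 3: week 3 + 1 + 3 = 7.
- Assessment 4: week 7 + 1 + 3 = 11.

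The look-backs are 3, 7 − 3 = 4 and 11 − 7 = 4 weeks. The last two each contain one washout week in the participant's own shoes, followed by three weeks with one study device.

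**3. Weekly contacts already planned.** There are about 11 over the 11 weeks: 9 in wear weeks and 2 in washout. Of these, 11 − 3 = 8 do not coincide with an assessment.

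**4. Content of those contacts (section 5.5).**
- Brief Pain Rating: three items (pain now, average this week, maximum this week).
- Qualitative assessment: liking, willingness to continue and preference, each with an open prompt for reasons.
- Check-in: content not defined; it may be a call, an email or an app message.
- Washout weeks: pain rating only.
- No written item on falls, blisters or skin breaks. The procedures listed for Assessment 2, and repeated at Assessments 3 and 4, include no adverse-event item either, so asking at assessments rests on section 6.0 alone.

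**5. What participants are told to report.** Between visits they are asked to get in touch with questions or if the footwear hurts or is uncomfortable. If an increase in pain worries them, they are to leave the study or see their own clinician. Falls are not named.

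**6. Why the footwear must be asked.** In the acclimation week, daily wear rises from 1 hour on day 1 by one hour a day. The period alone therefore does not show what was on the foot when an event occurred.

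**7. After the fix.** Using the existing contacts gives about 11 collection points with one-week look-backs, in place of 3 points with look-backs of 3 to 4 weeks. No new contact is needed.

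**8. Size.** The documents give neither an event rate nor a capture rate. Purely as an illustration, assume a per-participant event risk of 5% to 10% and capture of 100% or 50%. The chance of recording at least one event is 1 − (1 − risk × capture)^n:

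| n | Risk | Full capture | Half capture |
|---|---|---|---|
| 25 | 5% | 72% | 47% |
| 25 | 10% | 93% | 72% |
| 100 | 5% | 99% | 92% |

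Here 25 is the number of completers in the power section and 100 is the ankle OA enrollment target, not all of whom need be in a take-home group. The risks and capture rates are assumptions.

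**The case against.** The strongest reply is that the participant has several other routes to staff. The weekly contact includes a check-in, the qualitative questions ask for reasons in open form, wear periods bring two messages a day, and participants are told to report painful footwear. A painful blister would often come to light. This stands in part and is why the size is unknown. But the check-in is undefined, none of these routes is linked to adverse-event recording, and none is directed at falls.

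A second reply is that no hypothesis is a safety hypothesis and section 6.0 plans only a list. That limits the consequence, but a list meant for comparison with the literature still needs known ascertainment.

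A reader might go further than the documents allow in four ways:
- **Group 4 has only spontaneous calls.** It has three remote follow-up assessments in the same numbered sequence as the other take-home groups. The gap is that section 6.0 does not say they count, or how skin would be checked remotely. That under-counting is worst in this group is plausible but not shown.
- **Falls are never asked about.** Section 6.0 says safety data are collected at visits on IRB forms that are not in the documents. What is asked there cannot be determined.
- **Three assessments cover only 3/11 = 27% of the time.** That assumes an event is visible for one week, is not recalled later and prompts no call.
- **Events will be credited to the wrong device, or groups cannot be pooled.** Each look-back contains only one study device, and no pooled event-rate analysis is planned. Comparability between remote and on-site participants is uncertain, no more.

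**Conclusion.** The point holds as a gap in safety ascertainment. Between assessments at about weeks 3, 7 and 11, collection is passive; two named risks have no stated question at the weekly contact; and the status of group 4's remote assessments is undefined. Events are at risk of being missed or poorly dated. A reader might infer that they will be under-counted by a known amount, but without an event rate or a capture rate the documents do not support that.

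The effect falls on the planned tabulation, literature comparison and attribution of risk. It also leaves the statement about fall risk without a dedicated fall question behind it. The efficacy and range-of-motion analyses are unaffected. The change is worth making because it is cheap, not because the study fails without it. The conclusion rests on reading section 6.0 as the full collection rule and on the schedule running as planned.

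**What to change.** Amend section 6.0 so that safety data are also collected at each existing weekly contact in groups 2, 3 and 4, washout weeks included. Add two fixed yes/no items: any fall this week; any blister or skin break this week. For a yes, record the date and the footwear worn at the time, and open the existing log or form. Ask the items alongside the Brief Pain Rating, not inside it, so that the pain instrument is unchanged. State in section 6.0 that group 4's remote assessments are safety collection points.

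The cost is two short items on a call, email or app message already sent. The drawback is that more minor events will be logged. Anticipated ones go on the log sheet that section 6.0 already provides for annual reporting, but the review required after each adverse-event report would be triggered more often, and the team should plan for that. A further contact after Assessment 4 is optional: the study footwear is returned then, and nothing in the documents requires it.

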We will take video and photos of participants during portions of this study for documentation and use in research publications. All videos and photos will be anonymized (to avoid facial or voice identification) and tattoos and other distinguishing marks will be covered before images are captured or obscured during processing to protect the identity and privacy of our participants.

During study sessions, visitors and observers will not be allowed in the lab unless the participant agrees to their presence; the participant can change her/his mind at any time.

Study Footwear

Over the course of the study (one day or ~3 months) participants will be asked to wear up to three different footwear conditions: control shoes (a typical walking shoe, such as the New Balance 928), RB shoes (walking shoes with a front-to-back curved sole, such as the New Balance 928 with a rocker sole), and an orthotic device (such as an AFO, an ankle brace, such as the Toeoff[®] AFO) with control shoes. Participants will wear each footwear condition, in a randomized order. For all footwear conditions a fitbit zip may be clipped or taped to the shoe. This will record steps taken in the footwear. The fitbit will be synced during the VA visits and will only record number of steps. A separate account for each fitbit will be created and the account number will be recorded on the participant crosswalk. There will be no additional methods to link the data to the participant. Additional assessments on the initial day may include barefoot and own shoe as footwear conditions.

Screening /Eligibility Verification

Participants will have been preliminarily screened during recruitment, then during the first visit, after informed consent, we will make a final eligibility determination. This will include verifying that the information collected during recruitment is accurate and current.

If a participant cannot continue in the study, they will be compensated \$50 for the visit.

Demographic Data collection

Participants' age, sex, race/ethnicity and Veteran status will be recorded.

Anthropometrics

Participants' weight, waist circumference, and height will be measured.

Pain/health screening

Short survey which will include questions regarding trauma history in the lower limbs, joint replacements, OA, and pain throughout the body.

Functional Assessments

Self-selected Walking Speed (SSWS)

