Over the course of the study, participants with ankle OA will repeat the biplane fluoroscopy session 3 times (once for each footwear condition). Participants in study group 1 will complete the biplane in one session while barefoot, or wearing their own shoes, the control shoes, RB shoes, and/or the AFO. Each participant will receive no more than 80 total biplane imaging trials as part of the study.

Participants enrolled in study group 3 will continue wearing the StepWatch. Those in study group 1 have completed their participation and will return the study footwear and StepWatch.

Take home study

Length of participation

For participants with ankle OA, study procedures will occur over ~3 months (11 weeks). Four study visits will be done at the VA Puget Sound where three at-home/in-community study footwear (control shoes, RB shoes, an AFO) condition periods will be conducted.

Visits at the VA Puget Sound may last up to 4 hours each. Participant schedules and the accessibility of facility resources may extend the study timeframe beyond these estimates. Study visits will be scheduled by contacting the participants on phone, or during in-person contacts. We may contact participants with appointment and/or at home activity reminders via email or phone.

Assessment 1

During this initial assessment participants will complete the, Screening, Functional assessments, LineUP with pregnancy test (not Study group 4), Questionnaires, and Brief Pain Rating. Participants will be given a StepWatch and the first footwear condition. At the first assessment, participants who elect to use Ilumivu will be assigned a randomized username for the ilumivu mobile application. The link between this unique ID and the Veteran's identity will not be stored in the mobile application, but rather, stored locally at the Seattle VA. Further information about data security can be found in the Data Security section of this application. Ilumivu, is an app downloaded onto your phone. This app and its developers do not have any information that can be linked back to the participant. Only the researchers will know the Ilumivu participant ID. The Ilumivu participant ID will be recorded on the participant crosswalk in the research folder on the R drive. There will be no additional methods to link the data to the participant.

In Home/Community - Footwear Condition 1: Acclimation and Continuous Wear Period (3 weeks)

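### Section 6.0 promises to attribute added risk to the protocol, but adverse events other than pain have no planned breakdown by footwear, only a list set against the literature

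*Combined protocol and SAP*

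**What the plan says.** Section 6.0 Reporting describes how AEs are gathered, summarised and interpreted.

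- Collection: "This information will be collected at study visits and whenever participants call to report a problem", and "Safety data will be collected on an as-needed basis and will begin upon enrollment into the study".
- Summary: "we will tabulate a list of any such reports that occur during the study and compare it with corresponding data available in the literature".
- Pain: "Participant pain ratings will be collected weekly which will help us to monitor any significant changes".
- Conclusion, in the very next sentence: "This will allow us to analyze how much of an increased risk was due to the administered protocol".

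Section 5.5 sets out the design. Under Study Footwear: "Participants will wear each footwear condition, in a randomized order". Under Take home study, for participants with ankle osteoarthritis (OA): "three at-home/in-community study footwear (control shoes, RB shoes, an AFO) condition periods will be conducted". One week in the participant's own footwear follows each of the first two periods. The risk subsection of 5.5 names falls, soft tissue irritation and skin breakdown at home, and says of pain: "There is a risk that the study assigned footwear could increase foot or ankle pain".

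Section 5.6 (Statistical Methods) models step count, walking speed, physical function, pain and joint range of motion by footwear. It contains no analysis of AEs.

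**The concern.** The summary in section 6.0 does not lead to the conclusion stated there. A list compared with published data has no matched reference. Published groups will differ in eligibility, wear schedule and the way events are sought, and as-needed collection makes their rates especially hard to match. Even a fair match would say little about which footwear was responsible unless events are placed against the footwear worn at the time.

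The Introduction says the study should inform clinical choices about RB shoes and AFOs. As planned, benefit would be reported by footwear, while falls, skin problems and intolerance would not. An excess confined to one device could disappear into an overall count that also contains control-shoe periods and own-shoe weeks.

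**Working it through.** The plan gives no AE rate, safety sample size or safety error level, so there is no figure to reproduce. The check has three parts.

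**1. Which harms have an internal comparison?** Setting sections 5.5, 5.6 and 6.0 side by side:

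| Harm | Summary stated in the plan | By footwear? |
|---|---|---|
| Increased pain | Weekly ratings (6.0); mixed model with contrasts against the control shoe (5.6, Aim 1) | Yes |
| Falls | List and literature (6.0) | Not stated |
| Skin irritation or breakdown | List and literature (6.0) | Not stated |
| Fit failure, early move to the next condition, withdrawal | No summary stated | Not stated |

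**2. Can an event be placed in a period?** The schedule is 3 footwear periods × 3 weeks + 2 washouts × 1 week = 9 + 2 = 11 weeks, which matches the stated length of participation. An event with an onset date can therefore be assigned to control shoe, RB shoe, AFO or own-shoe washout. Scheduled exposure for n completers is 3n person-weeks per footwear and 2n in washout:

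- n = 25 (minimum expected under Power Analysis): 75 per footwear, 50 in washout.
- n = 100 (all OA participants in the abstract): 300 per footwear, 200 in washout. This is a ceiling for the take-home part, because one study group attends for a single day.

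**3. What would a breakdown show, and how precisely?** All risks here are assumptions for illustration.

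*Dilution.* Suppose the per-period risk is 5% in two conditions and 15% in one device, with one event per affected period and none in washout. The average per-period risk is (5 + 5 + 15)/3 = 8.3%. At n = 100:

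- by condition: 5/300, 5/300 and 15/300, that is 1.7, 1.7 and 5.0 per 100 person-weeks;
- all footwear together: 25/900 = 2.8 per 100 person-weeks;
- with washout included: 25/1100 = 2.3 per 100 person-weeks.

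The threefold excess is visible only by condition.

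*Precision.* For control-shoe risk pc and device risk pt, with events assumed independent between a person's periods, let d = pt − pc, p10 = pt(1 − pc) and p01 = pc(1 − pt). The 95% half-width of the paired difference is 1.96 × √[(p10 + p01 − d²)/n].

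For 5% against 15%: p10 = 0.1425, p01 = 0.0425 and d² = 0.01. At n = 25 this gives 1.96 × √(0.175/25) = 0.164.

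Half-width in percentage points, with exact two-sided McNemar power at 0.05 in brackets:

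| Assumed risk, control / device | n = 25 | n = 30 | n = 100 |
|---|---|---|---|
| 5% / 15% | 16.4 (6%) | 15.0 (10%) | 8.2 (59%) |
| 5% / 25% | 19.0 (32%) | 17.3 (44%) | 9.5 (98%) |
| 10% / 30% | 21.5 (28%) | 19.6 (36%) | 10.7 (93%) |

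Positive correlation between a person's periods would narrow these intervals. At the sizes in the power section, the table can describe but not test.

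**The case against.** The strongest reply is that section 6.0 does not rely on the list alone. The attribution sentence directly follows the weekly pain ratings, and pain is itself a named footwear risk. Section 5.6 compares it between control shoe, RB shoe and AFO within participants. That stands: a reader might infer that no safety outcome is compared by footwear, and for pain that is wrong. The answer is partial, however. Mean pain does not count people harmed, and someone who cannot tolerate a device may move on early and contribute little or no end-of-period data for it.

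A reader might also infer that events will be pooled into one rate. The text says only that reports will be listed. The forms and log are not in the documents, and nothing says that date or footwear is left off. The supportable point is that no breakdown is planned.

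Next, the control shoe is itself study footwear, and the protocol also includes imaging and laboratory walking. A contrast with the control shoe therefore estimates the added risk of the RB shoe or AFO, not of the whole protocol. This also stands, and it limits what the remedy can claim. Own-shoe weeks come closer to a no-device reference, but carry-over is possible.

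Finally, section 6.0 concerns event reporting in a study it regards as low risk, no hypothesis depends on AE counts, and the comparison would be imprecise. This argues for descriptive reporting; it does not justify leaving the breakdown out.

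**Conclusion.** The point holds for AEs other than pain. The plan states no tabulation of these events by footwear, and comparison with the literature cannot attribute them to the RB shoe or AFO. The efficacy analyses are not affected.

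The documents do not support the stronger reading that the attribution aim is wholly out of reach, because pain has a valid internal comparison. Nor do they show that every take-home participant supplies a control-shoe period. Section 5.5 speaks of up to three conditions and lets a participant move on early when a comfortable fit cannot be achieved.

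The size of any hidden excess is unknown, since the plan gives no AE rates. The 8.3% average and the interval widths rest on assumed risks and, for the widths, on independence between periods. Half-widths of about 15 to 22 points at 25 to 30 participants, and 8 to 11 at 100, mean that the remedy improves attribution but will rarely settle it.

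**What to change.** In section 6.0, with a matching paragraph in section 5.6:

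1. For each AE in a take-home participant, record the onset date and the footwear worn at onset: control shoe, RB shoe, AFO or own-shoe washout.
2. Report events, participants with events and person-weeks of exposure by condition. Include falls, skin irritation or breakdown, fit failures, and early switching or withdrawal. Count the exposure actually accrued, so that shortened periods are handled correctly.
3. Give within-participant risk differences with confidence intervals for RB shoe and AFO against the control shoe, labelled descriptive.
4. Show the own-shoe washout weeks as a no-device reference, with a caveat about carry-over.
5. Keep the literature comparison as context only, and limit the attribution sentence to the added risk of RB shoe or AFO over the control shoe.

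The cost is one log field, if it is not already there, and one table, with no new visits or participants. Footwear at onset is best captured prospectively. The drawback is wide intervals, because events will be few.
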